5. Spouse, significant other, or other family member involved in decision making for child <18 years if parent/legal guardian of child already enrolled into this study.

Total number of subjects to be studied (including those screened for eligibility) in Qualitative Needs Assessment Interviews and Beta Testing:

Up to 50. Sample size is dependent on data saturation during analysis and need for verification of findings.

Total number of subjects to be studied in Hindi Beta Testing

Up to 50 individuals will be consented for participation in the Hindi Beta Testing study. Sample size is dependent on data saturation during analysis and need for verification of findings.

Total number of subjects to be studied (including those screened for eligibility) in Testing of Decision Aid:

Cohort A: 120

Cohort B: 25

Cohort C: Up to 50 (depending on number of health care providers providing care to patient population in this study).

Sample Size Calculations for the Randomized Clinical Trial (Cohort A)

We assume that patient involvement is 30% with standard care and we can double this with the intervention. Based on 90% power and 0.05 significance level we will require 110 patients, 55 in each group for comparing 2 binomial proportions⁴⁴. To account for attrition we propose to recruit 120 patients, 60 in each group treatment group with 20 in each of 3 age groups.

Total Duration of Participation

Qualitative Needs Assessment Interviews: 6 weeks

Decision Aid Testing: Up to 12 months

Recruitment Methods

Potential participants may be recruited from the Aflac Cancer and Blood Disorders Center of Children's Healthcare of Atlanta (Egleston, Hughes Spalding, and Scottish Rite locations) and the Georgia Comprehensive Sickle Cell Center at Grady Health System. Physicians will be notified via list-serves, at conferences and seminars of study recruitment. They will be asked to contact the study coordinator if interested in participating. We will provide patient recruitment flyers for placement in patient/parent/caregiver common areas in their office or clinic. Additionally, we will contact sickle cell foundations for assistance. We will ask that the recruitment flyers be placed on their websites. Recruitment flyers will request interested individuals to contact the research team if interested in participation. Discussion with physicians will occur prior to enrollment of subjects to obtain physician understanding of study. Patients and/or caregivers may be approached directly by research team members for participation in the needs assessment.

Flyers with study information for study sections will be provided to the clinics and to the healthcare providers.

Needs Assessment Interviews: Patients and/or caregivers may be approached directly by research team members for participation in the needs assessment. Physicians and other healthcare providers may also refer patients for possible participation. Potential participants may also contact the study coordinator directly using the contact information provided on the flyer if interested in hearing more about the study.

Hindi Beta Testing Recruitment

Health care providers will be notified by physicians involved in the study of the beta testing study. If interested, research staff will be notified and consent will be obtained if they desire participation. Physicians will be asked to identify potential patient and parent/caregiver participants. If potential participants agree to talk with research staff, the study will be introduced and, if interested, consent will be obtained.

Decision Aid Testing: Sickle cell healthcare providers who see patients at these sites will be provided with study information and asked to present the study to patients who are considering a therapy new to their care (chronic blood transfusion, hydroxyurea, bone marrow transplantation). After the healthcare provider obtains permission from the patient, a research team member will approach the patient to introduce the study.

Consenting

Needs Assessment Interviews: Potential participants may be introduced to the study by a member of the sickle cell healthcare team who will obtain permission for the individual to be approached by a member of the research team. Patients and/or caregivers may be approached directly by research team members for participation in the needs assessment. The potential participant may also directly contact the study coordinator via contact information provided on the study flyer. Screening for eligibility will be completed. If eligible, and the individual is interested, the consent will be verbally reviewed, including expected study activities, and potential risks and benefits. The individual will have an opportunity to discuss potential study participation with significant others, including caregivers and other family prior to consenting. All questions will be answered by a member of the research team and/or the PI. If the individual agrees to participate, he/she will be verbally consented in-person or via telephone.

Beta Testing

Potential participants will be introduced to the study by a member of their healthcare team who will obtain permission for the individual to be approached by a member of the research team. If permission is obtained for discussion with the research staff, the research staff will introduce the study. The consent will be reviewed. All questions will be answered. If the individual is interested in participation verbal consent will be obtained.

Decision Aid Testing: Potential participants will be introduced to the study by their primary sickle cell healthcare provider who will obtain permission for the patient to be approached by a member of the research team. The potential participant will be screened for eligibility. If eligible, and the individual is interested, the consent will be reviewed, including expected study activities, and potential risks and benefits. The individual will have an opportunity to take the consent home to discuss it with significant others, including caregivers and other family. The individual will also be given the opportunity to discuss it with his/her hematologist. All questions will be answered by a member of the research team and/or the PI. If the individual agrees to participate, he/she will be consented. A copy of the signed consent will be given to the participant.

Analytic Methods

Qualitative analysis will be performed using qualitative descriptive methods which is influenced and a similar to interpretive descriptive analysis. Qualitative descriptive^{45,46} analysis requires less interpretation than other types of qualitative analysis, such as phenomenological or interpretive description. Qualitative description lends itself to a more straightforward analysis that, by the nature of its methods, lends itself to this study. Analysis of these data will rely on components of the Ottawa Decision Support Framework for development of a codebook. This framework provides operational definitions of needs in the decision making process, such as decisional conflict (uncertainty), knowledge and expectations, personal values, and support/resources available. Additionally, data will be quantized or translated to numerical data for improved understanding of results⁴⁷. This method of analysis allows for quantification of themes, patterns, and idiosyncrasies unique to qualitative research that may otherwise be discarded as outliers in quantitative analysis⁴⁷.

We propose a randomized controlled trial of decision aid vs. usual care to determine its impact on previously defined endpoints measuring decisional process and decisional quality.

Avoidance of bias

Selection biases occur when the groups to be compared are different. We anticipate that randomization will avoid selection bias as well as volunteer or referral bias. A *drop out analysis will be carried out to determine the contribution of attrition bias*. Measurement biases involve systematic error that can occur in collecting relevant data and include, insensitive measure bias, expectation bias, recall or memory bias, attention bias, and verification or work-up bias. Systematic validation of the decision aid will avoid *insensitive measure bias* which occurs when instruments used are not sensitive enough to detect what might be important differences in the variable of interest. The risk of *Expectation bias*, when observers may err in measuring data toward the expected outcome will be avoided by masking or blinding the reviewer of the survey about the arm to which the patient was randomized. Recall or memory bias which can occur if outcomes being measured require that subjects recall past events will be avoided by administering surveys within days of the interaction with their health care provider.

Human Subjects

Protected Health Information

Name, address, telephone number, and email address (if appropriate) will be recorded to facilitate contact with study subjects and to mail gift cards. No other PHI will be collected or recorded.

Third Party Information

1. Information will be gathered from participants with sickle cell disease regarding individuals/family members (caregivers/parents/legal guardians) who assist with sickle cell healthcare decision making, including but not limited to relationship to participant, age, gender, marital status, education level of individuals/family members.
2. Parent/legal guardian of the child with sickle cell disease will be asked information including but not limited to their relationship to that child, the child's role in decision making regarding sickle cell healthcare, number of siblings the child has, demographic information such as gender, age, and education level of the child.

Potential Risks

There is a risk of breach of confidentiality. The web-based decision aid is maintained on a secure server and requires a unique individualized identification and password to log on. Users will be instructed to protect their log-on information, to not share it with anyone else, and to be aware of the presence of others when logging on to the site. All efforts will be made to avoid breach of confidentiality.

There is a risk of discomfort with qualitative interviews. The participant is not required to answer and question he/she does not feel comfortable answering. The participant may speak with the primary investigator, his/her physician or a member of the healthcare team as needed.

Potential Benefits

There are no direct benefits for participation in the Needs Assessment interviews though information learned may be used to benefit others in the future. There is a potential benefit of participating in Testing Decision Aid secondary to increased access to information that may increase the ability to make an informed values based decision regarding sickle cell treatment.

Data and Safety Monitoring Plan

Research staff directly involved in the study will have access to data collected during this study. Paper documents will be filed in a locked filing cabinet in a secure office setting. Electronic data will be maintained on a secure Hematology/Oncology share-drive with limited access behind a secure firewall at Emory University. Participant data will be identified with a unique number. The key connecting the participant to the ID number will be maintained separately from the study data and will be destroyed upon completion of the study, to include dissemination of findings. The ID key will be accessible only to members of the research team. All audio recordings will be identified on the recording with the unique participant identification number. All transcripts will be identified using the participant identification number and names of parents and health care providers will be indicated with "XXX" in the transcription. Audio transcriptions will be destroyed after transcription is complete and verified, analyzed and findings are disseminated.

The data and safety monitoring team will include the Principal Investigator and the study coordinator. Meetings will occur every 3 months from time of enrollment of the first patient. DSMP reports will be generated for each meeting. Any information regarding increased risks, modifications necessary to ensure patient safety, and adverse events will be discussed and submitted to the IRB according to established guidelines. All study data reviewed and discussed during these meetings will be kept confidential. Any breach in confidentiality will be reported to the IRB and regulatory agencies. The investigator will continue to review all available information and study results regarding this patient population. The PI will report to the IRB within 24 hours any serious adverse event occurring that is associated with this research study. Unexpected adverse events of moderate severity in association with the research intervention will be reported to the IRB within 5 business days. Reporting of adverse events to sponsors and federal agencies will be the responsibility of the investigator.

Withdrawal from Study

The participant may withdraw from the study at any time by notifying the PI and/or the research team. All data collected up until the point of withdrawal will be included in data analysis. No further data will be collected.

The participant may be withdrawn from the study if the participant does not participate in the educational process of usual care or if the participant assigned to intervention does not view the website prior to the next scheduled clinic appointment or does not show for the next appointment and does not reschedule that appointment within 4 weeks of the originally scheduled appointment.

Compensation

Study participants, (patients, parents/legal guardians) will be provided with a \$25 gift card for each completed set of survey questions.

Participants (patients, parents/legal guardians and caregivers) will be provided with a \$25 gift card for completion of each qualitative interview.

Healthcare providers and stakeholders will be given a sickle cell tie, bowtie or scarf for their participation in this study.

There will be no compensation provided for participation in the Hindi beta testing.

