2. Does the use of a decision aid result in improvement of patient knowledge, patient involvement in the decision, the congruence of their decision with their values and preferences?
3. Is the Hindi version understandable and useable by patients?

Expected Outcomes:

1. Collection and analysis of qualitative interviews using an open-ended semi-structure interview guide will provide understanding of patient and parent/caregiver knowledge, expectations, values, barriers and needed support that needs to be provided in a decision aid tool.
2. Based on the goals of the decision aid to provide accurate information to patients and caregivers about the risks and benefits of various treatments and to enable them to make informed and involved therapeutic decisions based on their values, preferences and stated goals we propose the following outcomes:
 - a) Impact on patient knowledge and understanding of treatment risks and benefits. Patient knowledge will be tested by using a knowledge questionnaire. Since knowledge is different from understanding we will design questions that test understanding e.g., if they understand the concepts and meaning for e. g., of an 80% survival by using different scenarios.
 - b) Impact of the decision aid on the decision making process and on the treatment decision, including the extent of patient involvement, the specific decision made, satisfaction with the decision-making process and with the decision. Patient involvement in decision making will be tested using a Patients' Perceived Involvement in Care Scale^{38,39}.
 - c) Psychological impact of decision aids on decisional burden, decisional conflict and decisional regret. Decisional conflict will be measured using a decisional conflict scale. Decisional conflict is evaluated using a validated decisional conflict scale^{40,41}. Decisional regret will be evaluated by using a validated decision regret scale⁴². Decisional burden will be evaluated using a validated decision burden scale⁴³.
 - d) Uptake, adherence and satisfaction with therapeutic option discussed. Within 4 months following discussion with the physician/healthcare provider we will also survey patients to determine their uptake, adherence with, and satisfaction with, the therapeutic option discussed.
3. The Hindi version of the decision aid will be comprehensible and useable as demonstrated by beta testing.

Methods

Study Design for Qualitative Interviews Decisional Needs Assessment

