We will collect demographic information from parent/legal guardian of children (<18 years of age) including but not limited to age, gender, race, education, marital status, employment and religion. Additionally we will collect demographic information about the child including but not limited to age, gender, race, education, number of full and half siblings). Additionally patients and parents/legal guardians of patients will be asked to self-report information regarding themselves or the patient they care for including but not limited to patient age, gender, education level, marital status, genotype, insurance type, history of HLA typing, number of hospitalizations for sickle cell related complications in the past 2 years. No PHI will be accessed.

Participants will be asked to complete the following study surveys at within 2 weeks following their office/clinic visit, questionnaires will be available in paper version and electronically:

- Acceptability of education (*8 multiple choice, 2 short answer*)
- Decision Self-Efficacy Scale (*11 multiple choice*)
- Decisional Conflict Scale (*16 multiple choice*)
- Values survey (*14 multiple choice, 6 fill in the blank*)
- Realistic Expectations (*multiple choice*)
- Preparation for Decision Making Scale (*10 multiple choice*)
- Knowledge Survey (*25 multiple choice*)
- Choice Predisposition and Decision (*1 multiple choice and 4 fill in the blank*)
- Stage of Decision Making (*10 multiple choice*)

Participants => 18 years of age will complete:

- Emotional distress Anxiety – short form 6a – participant version
- Depression – short form 6a – participant version
- Fatigue – short form 6a – participant version
- Pain interference – short form 6a – participant version
- Physical Function – short form 8b – participant version

- Ability to participate in social roles and activities – short form 6a – participant version

Participants of children <18 years of age will complete:

- Fatigue – short form 10 – parent proxy
- Mobility – short form 8 – parent proxy
- Peer relations – short form 7 – parent proxy
- Anxiety – short form 8b – parent proxy
- Depressive symptoms – short form 6b – parent proxy

It is anticipated that these surveys will take 20-30 minutes to complete within 2 weeks following each visit. Surveys may be available via paper version and electronically.

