Participants in Cohort A who are assigned to the control group will receive education regarding treatment consideration from their healthcare provider/team as per standard practice (usual care).

Participants in Cohort A who are assigned to the intervention group will receive education regarding treatment consideration from their healthcare provider/team as per standard practice. Additionally, they will be provided access to the decisional aid and will be provided with a unique access ID and password for purposes of this study. Participants will receive follow-up monthly via telephone call and/or e-mail to verify ability to access and navigate through website.

Visit 2

Participants will be scheduled for the second research visit to coincide with the completion of education presented by the healthcare provider/team. Participants will be asked to complete the study surveys within 2 weeks following the office/clinic visit via paper version or on-line. Self-report information regarding themselves or the patient they care for will be updated relating to sickle cell disease management and complications since Consent/Visit 1. Participants will receive follow-up monthly via telephone call and/or e-mail to verify ability to access and navigate through website.

Visit 3

Participants will be scheduled for the final research visit within 4 months of the completion of education and discussion with their healthcare provider/team. Participants will be asked to complete the study surveys as well as either via paper versions or online within 2 weeks following this office/clinic visit:

- Decision Regret Scale (*5 multiple choice*)
- Additionally, a qualitative interview will be conducted with the participants within 4 weeks of visit 3 to evaluate the extent to which the method of educational tools (standard practice or decision aid) helped the participant to recognize that a decision needs to be made regarding treatment of sickle cell disease, to understand the values that affect the decision, and understand if and how these values were addressed with the health care provider. Interviews will take approximately 30-45 minutes for completion. Interviews will

be audio recorded and transcribed verbatim for later analysis. Interviews will be conducted in a private setting, away from family members and clinical staff.

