Self-report information regarding themselves or the patient they care for will be updated relating to sickle cell disease management and complications since Visit 2.

Cross-Over

After completion of final study visits/surveys and data collection, participants in the control group for Cohort A will be offered opportunity to visit the Decision Aid website. Participants will be given 4 weeks to review this site, at which time they will be asked to complete a series of questionnaires via paper version or electronically:

- Acceptability of education (*8 multiple choice, 2 short answer*)
- Decision Self-Efficacy Scale (*11 multiple choice*)
- Decisional Conflict Scale (*16 multiple choice*)
- Stage of Decision Making (*10 multiple choice*)
- Values survey (*14 multiple choice, 6 fill in the blank*)
- Realistic Expectations (*multiple choice*)
- Preparation for Decision Making Scale (*10 multiple choice*)
- Knowledge Survey (*25 multiple choice*)
- Choice Predisposition and Decision (*1 multiple choice and 4 fill in the blank*)
- Decision Regret Scale (*5 multiple choice*)

Participants => 18 years of age will complete:

- Emotional distress Anxiety – short form 6a – participant version
- Depression – short form 6a – participant version
- Fatigue – short form 6a – participant version
- Pain interference – short form 6a – participant version
- Physical Function – short form 8b – participant version
- Ability to participate in social roles and activities – short form 6a – participant version

Participants of children <18 years of age will complete:

- Fatigue – short form 10 – parent proxy
- Mobility – short form 8 – parent proxy
- Peer relations – short form 7 – parent proxy
- Anxiety – short form 8b – parent proxy
- Depressive symptoms – short form 6b – parent proxy

A qualitative interview will be conducted within 4 weeks of completion of the questionnaires to understand participant-perceived comparison of supportive care in decision making versus use of the Decision Aid tool. Participants will be asked to discuss the affect, if any, on their treatment decision prior to use of the Decision Aid tool. Participants will receive follow-up monthly via telephone call and/or e-mail to verify ability to access and navigate through website after receiving access to the decision aid.

Cohort B

Consenting/Visit 1

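### Outcome 2(c) promises a decisional burden scale, but no survey list includes one, so the arms cannot be compared on burden as the protocol names it

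*Combined protocol and SAP*

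**What the plan says.** Expected Outcomes, item 2(c), sets out this outcome: "Psychological impact of decision aids on decisional burden, decisional conflict and decisional regret". It assigns a validated scale to each construct. For burden the commitment is "Decisional burden will be evaluated using a validated decision burden scale", with a literature citation but no instrument title.

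The data collection sections then say when surveys are given.

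- **Cohort A, Consenting/Visit 1** opens its list with "Participants will be asked to complete the following study surveys at within 2 weeks following their office/clinic visit". The Decisional Conflict Scale is on it.
- **Cohort A, Visit 2** refers back to the same set: "Participants will be asked to complete the study surveys within 2 weeks following the office/clinic visit via paper version or on-line". It adds no instrument.
- **Cohort A, Visit 3** refers back again and adds one scale, the "Decision Regret Scale", and a qualitative interview.
- **Cross-Over** (control group, after final data collection) has its own list: "Participants will be given 4 weeks to review this site, at which time they will be asked to complete a series of questionnaires". Conflict and regret are both on it.
- **Cohort B** and **Cohort C** have separate, shorter lists.

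None of these lists contains a burden scale. Burden is not mentioned again after Expected Outcomes. Analytic Methods refers only in general terms to endpoints defined earlier.

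**The concern.** An outcome is stated in definite terms, and the schedule that should deliver it leaves it out. This is more than missing detail. Sites work from the survey lists, and a site following them exactly would collect no burden data in either arm.

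The loss could not be made good later. A self-report scale not given around the provider discussion and at the final visit cannot be reconstructed from other records. At reporting, the trial would either have to leave a stated outcome unreported without explanation, or put forward some other measure as burden after the data had been seen.

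**Working it through.** **Inputs.** The three constructs come from Expected Outcomes 2(c). The instruments come from the survey lists under Cohorts A, B and C. The planned numbers come from the sample size section: 120 in Cohort A, 60 per arm, 20 per arm in each of three age groups.

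**Step 1: set the promise beside the schedule.**

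| Place | Instruments listed | Conflict | Regret | Burden |
|---|---|---|---|---|
| Cohort A, Visit 1 | 9 decision instruments, plus 6 participant or 5 parent-proxy short forms | yes | no | no |
| Cohort A, Visit 2 | same set, nothing added | yes | no | no |
| Cohort A, Visit 3 | same set plus regret | yes | yes | no |
| Cross-Over (controls) | 10 decision instruments plus the same short forms | yes | yes | no |
| Cohort B | Decision Self-Efficacy plus 6 pediatric short forms | no | no | no |
| Cohort C | 1 provider questionnaire on patient readiness | no | no | no |

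**Step 2: count.** Three constructs are promised and two have a scheduled instrument. Burden has one at 0 of 3 Cohort A visits, so data are planned from 0 of 120 participants.

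**Step 3: are the lists open-ended?** They do not read that way. Each is introduced as the surveys to be completed, and most instruments carry an item count. The protocol does use non-exhaustive wording, but for demographic and self-reported clinical items, not for the surveys. The lists show no gaps or redaction marks.

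**Step 4: does anything else stand in for burden?**

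- The anxiety and depression short forms measure general distress.
- Acceptability of education concerns the education received.
- The Visit 3 interview has stated aims: recognising that a decision is needed, understanding the values behind it, and whether the provider addressed them. Burden is not among them.

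Each may give an indirect signal. None is assigned to burden.

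**Step 5: does the sample size depend on this?** The plan has no figure for burden. Its one calculated figure, 110, is for patient involvement of 30% against 60%. With pooled proportion 0.45, two-sided alpha 0.05 (assumed, since the plan does not state sidedness) and 90% power:

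n per arm = [1.960·√(2·0.45·0.55) + 1.282·√(0.30·0.70 + 0.60·0.40)]² / 0.30² ≈ 55.7, so 56 per arm and 112 in total.

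This agrees with the stated 110 to within 2 patients. Burden does not enter it.

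**The case against.** The strongest reply is that the trial is not blind to psychological effects. Participants aged 18 or over complete anxiety and depression short forms in both arms. Taking parents as 20 × 2 = 40 of the 120, that covers at least the 80 adult patients (120 − 40 = 80). Conflict and regret are also measured, and Analytic Methods says qualitative data will be converted to numerical form. This stands. A reader might infer that the trial could say nothing about whether the aid harms or distresses its users; the documents do not support that. What is missing is burden as 2(c) names it.

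A reader might also infer that parents' own distress goes unmeasured, because the list headed for participants of children under 18 is all parent-proxy. The text does not settle this. Parents are adult participants in Cohort A, so the list for those aged 18 or over can be read as including them. The pain and physical function forms suggest it was written for patients, but that is an inference. The point made here does not depend on it.

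It is also fair to say that burden is secondary. It is absent from the hypothesis, Aim 2, research question 2 and the sample size basis. The Patients' Perceived Involvement in Care Scale, named in outcome 2(b), is likewise missing from the Cohort A lists, and involvement is what the trial is sized on. That limits the weight of the burden point but does not remove it.

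Finally, the protocol does not define burden, and the cited scale cannot be inspected here. Claims about what it would detect, or how long it takes, would go beyond the documents.

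**Conclusion.** The point holds as an internal inconsistency. Outcome 2(c) commits to measuring decisional burden with a validated scale, and no visit in any cohort schedules one. Two of three promised constructs are collected; the third is not collected from any of the 120 planned Cohort A participants. Followed as written, the trial cannot make a randomised comparison of decisional burden.

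The conclusion rests on two readings: that the survey lists are complete as printed, and that the references back at Visits 2 and 3 mean the Visit 1 set. Both are the natural readings, and nothing later in the document contradicts them. The conclusion does not extend to psychological effects in general. It leaves the hypothesis and the sample size untouched. It should be corrected, but it does not threaten the trial's main comparison.

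**What to change.** Either of two changes removes the contradiction.

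1. **Collect it.** Name the burden scale cited in 2(c) and add it to the Cohort A survey set in both arms at Visits 2 and 3. It should be completed by the decision-maker, meaning the adult patient or the parent. State which of the two visits is used for the between-arm comparison. Adding it at Cross-Over is optional: only former controls complete that list, so it would give no randomised evidence.
2. **Drop it.** Delete burden from 2(c) and state that the trial will draw no conclusion about it.

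The first option costs a protocol amendment and one more questionnaire in a set estimated at 20-30 minutes. The documents do not give the scale's length, so the added time should be checked before committing. The second option costs only the amendment and the loss of the outcome. Neither changes the sample size.
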